## Study Protocol and Statistical Analysis Plan

**Brief Summary**: This study aims to systematically measure the extent and patterns of automation bias among physicians when utilizing ChatGPT-40 in clinical decision-making.

Condition or disease: Diagnosis

Intervention/treatment: Other: ChatGPT-40

Phase: Not Applicable

#### **Detailed Description:**

Diagnostic errors represent a significant cause of preventable patient harm in healthcare systems worldwide. Recent advances in Large Language Models (LLMs) have shown promise in enhancing medical decision-making processes. However, there remains a critical gap in our understanding of how automation bias -- the tendency to over-rely on technological suggestions -- influences medical doctors' diagnostic reasoning when incorporating these AI tools into clinical practice.

Automation bias presents substantial risks in clinical environments, particularly as AI tools become more integrated into healthcare workflows. Although LLMs such as ChatGPT-40 offer potential advantages in reducing errors and improving efficiency, their lack of rigorous medical validation raises concerns about potentially amplifying cognitive biases through the generation of incorrect or misleading information.

Multiple contextual factors can exacerbate automation bias in medical settings: time constraints in highvolume clinical settings, financial incentives that prioritize efficiency over thoroughness, cognitive fatigue during extended shifts, and diminished vigilance when confronting diagnostically challenging cases. These factors may interact with psychological mechanisms that include the diffusion of responsibility, overconfidence in technological solutions, and cognitive offloading---collectively increasing the risk of uncritical acceptance of AI-generated recommendations.

This randomized controlled trial (RCT) aims to systematically measure the extent and patterns of automation bias among physicians when utilizing ChatGPT-40 in clinical decision-making. The investigators will assess how access to LLM-generated information influences diagnostic reasoning through a novel methodology that precisely quantifies automation bias. In this study, participants will be randomly assigned to one of two groups. The treatment group will receive LLM-generated recommendations containing deliberately introduced errors in a subset of cases, while the control group will receive LLM-generated recommendations without such deliberately introduced errors. Participants will evaluate six clinical vignettes randomly sequenced to prevent detection patterns. The flawed vignettes provided to the treatment group will incorporate subtle yet clinically significant errors that should be identifiable by trained doctors. This will enable investigators to quantify the degree of automation bias by measuring the differential in diagnostic accuracy scores between the treatment and control groups.

Prior to participation, all physicians will complete a comprehensive training program covering LLM capabilities, prompt engineering techniques, and output evaluation strategies. Responses will be evaluated by blinded reviewers using a validated assessment rubric specifically designed to detect uncritical acceptance of erroneous information, with greater score disparities indicating stronger automation bias. This naturalistic approach will yield insights directly applicable to real clinical workflows, where mounting cognitive demands may progressively impact diagnostic decision quality.

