## **Outcome Measures**

#### **Primary Outcome Measures:**

*Diagnostic reasoning* [Time Frame: Assessed at a single time point for each case, during the scheduled diagnostic reasoning evaluation session, which takes place between 0-4 days after participant enrollment.]

The primary outcome will be the percent correct for each case, ranging from 0 to 100%, where higher scores indicate better diagnostic performance. For each case, participants will be asked for their three leading diagnoses, findings that support each diagnosis, and findings that oppose each diagnosis. For each plausible diagnosis, participants will receive 1 point. Findings supporting the diagnosis and findings opposing the diagnosis will also be graded based on correctness, with 1 point for each correct response. Participants will then be asked to name their top diagnosis they believe is most likely, earning 9 points for a reasonable response and 18 points for the most accurate response. Finally participants will be asked to name up to 3 next steps to further evaluate the patient with 0.5 point awarded for a partially correct response and 1 point for a completely correct response. The primary outcome will be compared at the case-level between the randomized groups.

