#### **Power Analysis:**

The minimum target sample size of 50 participants (25 participants per arm) was predetermined based on a prior study. The power analysis, conducted using Python version 3.11.9 (Python Software Foundation), employed the statsmodels.stats.power module from statsmodels version 0.14.4 (Statsmodels Developers) and indicated that a total sample of 200 to 250 completed cases (approximately 4 to 5 cases per participant) would provide at least 80% power to detect an 8-percentage-point mean difference in diagnostic reasoning scores, assuming a two-sided  $\alpha$  of .05. The analysis employed mixed-effects models suitable for cluster-randomized designs, considering an intraclass correlation coefficient (ICC) ranging from 0.05 to 0.15 and a standard deviation of 16.2%.

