#### **Statistical Analysis:**

Descriptive analysis will be performed by comparing participant characteristics and automation bias behaviors between the treatment and control groups. Any categorical variables will be reported using counts and proportions, while continuous variables will be reported as means and standard deviations or, if their distribution is non-normal, as medians with interquartile ranges.

To understand automation bias behavior the following descriptive statistics will be reported for both the study groups:

• *Proportion of clinical vignettes in which participants accessed LLM suggestions: For each of the six vignettes, a binary indicator will be recorded (1 = participant clicked to view the LLM's suggestions; 0 = no access). The final measure is the mean proportion of vignettes (range 0–1) per participant for which suggestions were accessed.* 

- *Proportion of clinical vignettes in which participants copy-pasted LLM suggestions: For each of the six vignettes, a binary indicator is recorded:* 
  - 1 = participant directly copy-pasted the LLM's suggestion into their diagnostic answer (i.e., accepted verbatim without any edits)
  - $\circ$  0 = no direct copy-paste occurred

The final measure is calculated as the mean proportion of vignettes (range 0-1) per participant in which suggestions were copy-pasted.

• *Mean fraction of questions per vignette answered via direct copy-paste of LLM suggestions*: For each vignette, we will calculate the fraction of questions that were copy-pasted by dividing the number of copy-pasted answers by the total of five questions per vignette. The final measure is the average of these vignette-level fractions across all six vignettes, yielding a single measure per participant that ranges from zero (no copy-pasting) to one (all questions copy-pasted).

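### The between-arm score gap estimates the effect of partly erroneous versus unaltered advice; it is not a measure of automation bias, and no outcome records whether the planted error was adopted

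*Combined protocol and SAP*

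**What the plan says.** The Detailed Description presents the between-arm difference in diagnostic score as the way to quantify automation bias, "with greater score disparities indicating stronger automation bias". It describes the rubric as "specifically designed to detect uncritical acceptance of erroneous information".

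Under Arms and Interventions, both arms see the same six vignettes with LLM recommendations and conventional resources. In the treatment arm, three of the six recommendations carry deliberately inaccurate information. In the control arm, none does. There is no arm without LLM advice.

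The primary score gives points for plausible diagnoses, correct supporting and opposing findings, the top diagnosis ("earning 9 points for a reasonable response and 18 points for the most accurate response") and next steps. The secondary outcome uses the top-diagnosis item alone, scored 18, 9 or 0.

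The Statistical Analysis section adds three descriptive behaviour measures: whether suggestions were opened, whether any were pasted, and the fraction of questions pasted. Pasting means text "accepted verbatim without any edits", and all three measures are averaged over the six vignettes. The same section describes the treatment effect more carefully, as that of access to recommendations of which some are inaccurate.

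**The concern.** Automation bias, as the Detailed Description defines it, is over-reliance on the tool's suggestions. A score gap against an arm that receives unaltered advice can arise in two ways: treatment-arm doctors follow the wrong advice, or they recognise it as wrong and do without help that the control arm had. Only the first is automation bias.

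The answers could tell the two apart if someone recorded whether the planted error appears in them, but no defined outcome does so. A wrong top diagnosis scores 0 whether it is the planted one or the doctor's own mistake. At stake is the trial's headline conclusion: a clear difference in score would not by itself show how far doctors followed wrong advice.

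**Working it through.** **1. The plan's own figure.** The Power Analysis gives these inputs: "The minimum target sample size of 50 participants (25 participants per arm"), 4 to 5 completed cases each, two-sided alpha 0.05, and "considering an intraclass correlation coefficient (ICC) ranging from 0.05 to 0.15 and a standard deviation of 16.2" points. It concludes that this "would provide at least 80% power to detect an 8-percentage-point mean difference in diagnostic reasoning scores".

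Effective n per arm = 25m / (1 + (m − 1) × ICC). Power = Φ(8 / (16.2 × √(2/n)) − 1.96).

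- m = 4, ICC 0.15: n = 100/1.45 = 69.0, power 82.6%
- m = 4, ICC 0.05: n = 100/1.15 = 87.0, power 90.3%
- m = 5, ICC 0.15: n = 125/1.60 = 78.1, power 87.0%
- m = 5, ICC 0.05: n = 125/1.20 = 104.2, power 94.6%

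The stated power reproduces. It is power for a score gap, whatever causes the gap.

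**2. What the gap contains.** On a flawed-set vignette let C be the mean score with unaltered advice, F the mean score with flawed advice, and U the mean score with conventional resources only. Then

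C − F = (C − U) + (U − F),

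that is, lost benefit plus harm relative to no advice. The trial observes C and F but not U. If the three accurate vignettes do not differ between arms, the six-vignette gap is (C − F)/2, so the 8-point target corresponds to 16 points on the flawed set. Take C = 80 and F = 64 as an illustration (the documents give no such scores):

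| U | Lost benefit | Harm | Six-vignette gap |
|---|---|---|---|
| 80 | 0 | 16 | 8 |
| 75 | 5 | 11 | 8 |
| 70 | 10 | 6 | 8 |
| 65 | 15 | 1 | 8 |

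The observed result is the same in every row.

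**3. Possible size of the lost-benefit part.** The documents give no unaided score and no maximum score, so this rests on assumptions.

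- Maximum score: 3 (diagnoses) + 18 (top diagnosis) + 3 (next steps) = 24, plus findings. One supporting and one opposing finding for each of three diagnoses adds 6, giving 30. Three of each adds 18, giving 42.
- Gain in the most-accurate rate from correct advice: 0 to 25 percentage points.
- Doctors who reject the error lose all of that gain, and other score items do not change.

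Lost benefit on the flawed set = gain × points lost / maximum × 100, halved over six vignettes. At the top of the range:

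- 18 to 0, maximum 30: 0.25 × 18/30 × 100 = 15; halved, 7.5
- 18 to 0, maximum 42: 0.25 × 18/42 × 100 = 10.7; halved, 5.4
- 18 to 9, maximum 30: 0.25 × 9/30 × 100 = 7.5; halved, 3.75
- 18 to 9, maximum 42: 0.25 × 9/42 × 100 = 5.4; halved, 2.7

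At the bottom, a gain of 0 gives 0 throughout. The ranges are therefore 0 to about 7.5 and 0 to about 3.75 points.

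For scale, with six cases per participant, effective n is 150/1.75 = 85.7 (ICC 0.15) to 150/1.25 = 120 (ICC 0.05). A six-vignette gap of 4 points would then be significant with probability 37–48%, and one of 6 points with probability 68–82%, even if no error had been adopted.

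**4. Whether any other planned analysis separates the parts.**

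- Primary, secondary and sequential-trend models: all use the same correctness scores.
- Within-subject contrast (Exploratory Analyses): with A the accurate-set mean, equal in both arms, it is (A − F) − (A − C) = C − F. This isolates the flawed set but keeps both components.
- Question-level descriptive comparison: shows where points are lost, not which answer replaced the correct one.
- Standalone LLM against control: says nothing about adoption in the treatment arm.
- Copy-paste measures: miss edited or retyped text. Because they average over six vignettes, pasting an error is not distinguished from pasting sound advice.

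**The case against.** The strongest defence is that the analysis itself is sound. The Statistical Analysis section describes the treatment effect as that of access to partly inaccurate recommendations, and randomization supports that estimate. The overclaim lies in the interpretive wording. This stands: a reader might infer that the primary comparison is invalid, and the documents do not support that.

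Second, a reader might infer that a doctor who rejects a planted error drops to unaided performance. The plan does not say so. It describes the errors as subtle, so the rest of a recommendation may still help, and conventional resources remain available. Performance after rejection could lie anywhere from unaided to fully aided. The control advice is also described only as free of deliberate errors, so its benefit may be small.

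Third, a reader might put a minimum on the lost-benefit share. A 10-point gain with an 18-to-0 loss and a 42-point maximum gives 0.10 × 18/42 × 100 / 2 = 2.1 points, or 27% of the target. That floor comes entirely from the assumed 10 points; nothing in the documents excludes zero.

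Fourth, the rubric is said to detect uncritical acceptance, and access and pasting are reported as automation bias behaviour. But the listed scoring items contain no such element. It would also be wrong to infer that verbatim adoption of the error is at least counted, because the pasting measures pool all six vignettes.

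Finally, the plan speaks of inaccurate information, not of one discrete wrong diagnosis per flawed vignette. Any adoption code must allow for that.

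**Conclusion.** The point holds as a mismatch between what is estimated and what is claimed. The score gap is a valid estimate of the effect of partly erroneous versus unaltered advice. Its size cannot be read as the degree of automation bias, because it includes any lost benefit of correct advice and no planned outcome records adoption of the planted error.

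The contribution of lost benefit is unknown. Under the assumptions shown it runs from nothing to 94% of the 8-point target (7.5/8) if lost diagnoses fall to 0 points, or to 47% (3.75/8) if they fall to 9. The upper ends combine the largest assumed gain, the smallest maximum score and complete loss of help after rejection; they are illustrations, not estimates. Reaching the full 8 points with no adoption would need correct advice to be worth 16 points on the flawed set, just beyond the 15 at the top of the assumed range.

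**What to change.** 1. Describe the score gap as the effect of erroneous versus unaltered advice, and remove wording that equates its size with automation bias. This costs only text.
2. Report the access and copy-paste measures separately for the three flawed-set and the three accurate vignettes, in both arms. The indicators are already recorded per vignette.
3. After scores are locked, have the masked graders code the existing flawed-set answers in both arms (50 × 3 = about 150 responses). The code is whether the planted erroneous element (diagnosis, finding or next step, as applicable) appears, whether pasted, edited or paraphrased. Where it is a diagnosis, also code whether it is the top choice. The control arm gives the spontaneous rate.
4. Compare adoption between arms with a mixed logistic model. Name a fallback for the case where control adoption is near zero: a penalized model, or a participant-level exact or permutation test. Study Design records completion on July 15, 2025, so label this outcome exploratory or post hoc if it is added after unblinding.

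The costs are one more outcome and a modest amount of grading. Graders who know the planted errors may infer the arm from a matching answer. Locking the scores first protects the scores but not the adoption code, and the report should say so.

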## Study Design

Study Type: Interventional (Clinical Trial)

Actual Enrollment: 50 participants

Allocation: Randomized. Randomization list was created by [name] using the Sealed Envelope program.

Intervention Model: Parallel Assignment

Intervention Model Description: The trial will be designed as a randomized, two-arm, single-blind parallel group study.

Masking: Single (Outcomes Assessor)

Masking Description: The grading of responses will be performed by assessors blinded to participant identity and treatment assignment.

Primary Purpose: Diagnostic

Official Title: Trust or Verify? Automation Bias in Physician-LLM Diagnostic Reasoning

Actual Study Start Date: June 5, 2025

Actual Primary Completion Date: July 1, 2025

Actual Study Completion Date: July 15, 2025

#### Arms and Interventions

Arm	Intervention/Treatment
Active Comparator: ChatGPT-40	Other: ChatGPT-40 Recommendations with
Recommendations with Hallucinations	Hallucinations
Participants will evaluate six clinical vignettes.	
During the trial, they will have access to clinical	ChatGPT-40's differential diagnoses of six clinical
recommendations from a specific, commercially	vignettes, three of which will contain deliberately
available LLM (ChatGPT-40) in addition to	introduced inaccurate information.
conventional diagnostic resources. LLM	*
recommendations for three vignettes will contain	
deliberately flawed diagnostic information and for	
three vignettes it will contain accurate	
recommendations). The cases will be presented in	
random order.	
No Intervention: ChatGPT-40 Recommendations	
without Hallucinations	
Participants will evaluate the same six clinical	
vignettes as in the intervention arm. During the	
trial, they will have access to clinical	
recommendations from a specific, commercially	
available LLM (ChatGPT-40) in addition to	
conventional diagnostic resources. However, the	
LLM-generated recommendations will not contain	
any deliberately introduced errors. The cases will	
be presented in random order.	

## **Outcome Measures**

#### **Primary Outcome Measures:**

*Diagnostic reasoning* [Time Frame: Assessed at a single time point for each case, during the scheduled diagnostic reasoning evaluation session, which takes place between 0-4 days after participant enrollment.]

The primary outcome will be the percent correct for each case, ranging from 0 to 100%, where higher scores indicate better diagnostic performance. For each case, participants will be asked for their three leading diagnoses, findings that support each diagnosis, and findings that oppose each diagnosis. For each plausible diagnosis, participants will receive 1 point. Findings supporting the diagnosis and findings opposing the diagnosis will also be graded based on correctness, with 1 point for each correct response. Participants will then be asked to name their top diagnosis they believe is most likely, earning 9 points for a reasonable response and 18 points for the most accurate response. Finally participants will be asked to name up to 3 next steps to further evaluate the patient with 0.5 point awarded for a partially correct response and 1 point for a completely correct response. The primary outcome will be compared at the case-level between the randomized groups.

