## **Secondary Outcome Measures:**

*Top choice diagnosis accuracy score* [Time Frame: Assessed at a single time point for each case, during the scheduled diagnostic reasoning evaluation session, which takes place between 0-4 days after participant enrollment.]

The secondary outcome will measure participants' performance in identifying the most likely diagnosis for each clinical vignette. After evaluating each case, participants will select their single most likely diagnosis, which will be scored on a pre-specified Three-Tier Diagnostic Accuracy Scale: 18 points for the most accurate diagnosis, 9 points for a clinically reasonable alternative, and 0 points for an incorrect diagnosis. For each participant, a Top Choice Diagnosis Accuracy Score is calculated as (total points earned  $\div$  maximum possible points) × 100, yielding a 0–100 % range in which higher scores indicate greater diagnostic accuracy. This percentage score will be compared at the case-level between randomized groups to quantify the impact of automation bias on diagnostic decision-making.

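### Does the primary percent score need a stated maximum and a stated limit on graded findings before it can be analysed?

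*Combined protocol and SAP*

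**What the plan says.** Primary Outcome Measures defines the scale: "The primary outcome will be the percent correct for each case, ranging from 0 to 100" percent. Participants give three leading diagnoses, each worth 1 point if plausible, and list findings for and against each one. On the findings it says: "Findings supporting the diagnosis and findings opposing the diagnosis will also be graded based on correctness, with 1 point for each correct response". The top choice is scored 0, 9 or 18, "earning 9 points for a reasonable response and 18 points for the most accurate response". For the last item, "participants will be asked to name up to 3 next steps to further evaluate the patient", at up to 1 point each.

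The Detailed Description says that blinded reviewers will mark the responses "using a validated assessment rubric specifically designed to detect uncritical acceptance of erroneous information", "with greater score disparities indicating stronger automation bias". The rubric is not reproduced. Study Design repeats that assessors do not know participant identity or arm. Statistical Analysis puts the scores on a 0–100 scale, again with no raw maximum. By contrast, Secondary Outcome Measures gives a formula ("For each participant, a Top Choice Diagnosis Accuracy Score is calculated as" points earned over maximum points, times 100), and its maximum of 18 per case can be read off. The Power Analysis says that 200 to 250 completed cases "would provide at least 80% power to detect an 8-percentage-point mean difference in diagnostic reasoning scores".

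**The concern.** Every item has a ceiling except the findings: 3 points for diagnoses, 18 for the top choice, 3 for next steps. The maximum is therefore 24 plus an amount that the text does not give, and percent correct has no stated denominator. The limit also sets how heavily the top diagnosis counts against the rest of the answer.

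This seems to matter because the Detailed Description reads the size of the score difference as the amount of automation bias, and because the planning difference (8 points) and SD (16.2%) are expressed on this scale. If the person computing the score had to pick a limit, the same answers could give different estimates and sometimes a different significance verdict. If the limit were picked after scores by arm were seen, the type I error rate would rise. It is also unclear whether a case with few findings listed counts as completed for the primary analysis.

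**Working it through.** **Inputs from the documents.** Three diagnoses at 1 point; top choice 0/9/18; up to 3 next steps at 1 point; six vignettes, three of them flawed in the treatment arm; 25 participants per arm; 8-point difference; SD 16.2%; ICC 0.05 to 0.15; two-sided alpha .05.

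**Assumed.** k findings of each kind graded per diagnosis, with k = 1, 2 or 3.

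**The plan's own power figure.** Effective cases per arm = N / [1 + (m − 1) × ICC] / 2, followed by a normal two-sample test.
- 200 cases, m = 4, ICC 0.15: 200 / 1.45 / 2 = 69.0; SE = 16.2 × √(2/69.0) = 2.76; 8/2.76 = 2.90; power 82.6%. At ICC 0.05: 90.3%.
- 250 cases, m = 5: 94.6% at ICC 0.05 and 87.0% at ICC 0.15.
- With a t reference on 48 df, the lowest of these is 81.1%.

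The claim of at least 80% therefore reproduces on the scale as planned.

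**What the limit does to the scale.** Maximum M = 3 + 3k + 3k + 18 + 3 = 24 + 6k.

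| k | M | Top-choice share, 18/M | One 9-point step | 8 percentage points in raw points |
|---|---|---|---|---|
| 1 | 30 | 60.0% | 30.0 | 2.40 |
| 2 | 36 | 50.0% | 25.0 | 2.88 |
| 3 | 42 | 42.9% | 21.4 | 3.36 |

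**What it does to the arm difference.** Suppose 27% of flawed-vignette top choices in the treatment arm fall from 18 to 0 (assumption). The mean raw loss per case is 18 × 0.27 × 3/6 = 2.43. Let f be the fall in the proportion of graded findings that are correct on flawed vignettes. The arm difference is then 100 × (2.43 + 6k × f/2) / (24 + 6k).

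| f | k = 1 | k = 2 | k = 3 |
|---|---|---|---|
| 0 | 8.10 | 6.75 | 5.79 |
| 0.10 | 9.10 | 8.42 | 7.93 |
| 0.20 | 10.10 | 10.08 | 10.07 |
| 0.40 | 12.10 | 13.42 | 14.36 |

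The limit makes no difference when f/2 = 2.43/24 = 0.101, that is, when findings lose the same share as the other items. Below that the difference shrinks as k rises; above it, it grows. The 29% shrinkage (5.79 against 8.10) belongs to the extreme row in which flawed advice leaves the findings untouched. If the limit applied per case and not per diagnosis, M would be 26, 28 or 30, and the f = 0 row would read 9.35, 8.68 and 8.10.

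**Significance.** A simulation of the same answers under each limit (25 per arm, six cases, effect on the top choice only, 15 assumed answer patterns) gave power of 61–84% at k = 1 and 43–69% at k = 3, with the two disagreeing on significance in 13–30% of trials. It is not calibrated to the plan. For top-choice rates of 10/20/70% (incorrect/reasonable/accurate), the mean is 14.4, the variance 243 − 14.4² = 35.64 and the SD 5.97, which is 19.9 percentage points at M = 30. The other two assumed patterns give 24.0 and 17.7. All three exceed 16.2 before any other item adds variation. The simulated ranges therefore do not describe this trial's power.

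**False positives.** With no effect, each scoring alone rejects in 4.4–5.6% of simulated trials; taking the best of three rejects in 6.1–7.3%.

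**The case for a change.** The best argument for a change is that the primary endpoint should be computable from the plan, and this one is not. The secondary outcome shows that the authors could write the formula. Blinded grading protects individual marks but not a denominator or cap chosen later. Stating the number would take a few sentences and no new data.

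The first part stands: a reader cannot recompute the score from the document alone. The rest is weaker. A common denominator only rescales the score and leaves the test statistic unchanged; what can alter inference is how many findings earn marks. The natural place to settle that is the marking itself, which is done blind to arm under the named rubric. A score that cannot exceed 100% also presupposes a fixed maximum. Nothing in the documents suggests that the limit was chosen with scores by arm in view, and the best-of-three inflation is modest even in that hypothetical case.

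The possible additions do not help much either. A rule scoring blanks as 0 might conflict with the complete-case analysis and with the multiple imputation planned for incomplete cases. What counts as a completed case is a separate question. The Power Analysis already says that the sample size was based on a cited prior study.

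**Conclusion.** The plan leaves out a detail but contains no wrong rule. The maximum and the number of graded findings are not stated. Under assumed limits of 1 to 3 per kind per diagnosis, the top diagnosis carries 60% to 43% of the score. Whether that raises, lowers or leaves unchanged the arm difference depends on how far flawed advice also affects the findings. Such an effect is plausible here, because the flawed material is a differential diagnosis and the plan tracks copy-paste across all five questions of a vignette. The stated power reproduces, and the planned descriptive comparison by question will show which items drive any difference.

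The conclusion rests on one inference: that the validated rubric, which the document names but does not reproduce, fixes the number of findings to mark. On that reading, graders and analysts fill the gap by applying the rubric, and writing the number into the plan would only transcribe it. The documents do not show that the primary result would be wrong, so no change follows.
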